3.4. Antidrug Antibody Only Analysis Set

The ADA only analysis set will include all patients rolling over from the pivotal efficacy studies for ADA assessment only.

4. GENERAL ISSUES FOR DATA ANALYSIS

4.1. General

Descriptive statistics for continuous variables include count (n), mean, standard deviation (SD), standard error (SE), median, minimum, and maximum. Descriptive statistics for categorical variables include patient counts and percentages.

Summaries of potentially clinically significant abnormal values will include all postbaseline values (including scheduled, unscheduled, and early termination visits).

Endpoint for safety analyses and summaries is the last observed postbaseline data (see Section 4.6 for the definition).

4.2. Specification of Baseline Values

For the patients rolling over from the pivotal efficacy studies, their baseline values will be the baseline values from the pivotal studies.

Eligible new patients will enter a 28-day run-in period during which they will complete daily electronic headache diary entries. The efficacy baseline values are based on the run-in period data. If the run-in period is greater than 28 days, the baseline values will be normalized to 28-day.

The efficacy variable baseline values during the 28-day run-in period that will be derived from the e-diary include

- total number of migraine days
- total headache days of at least moderate severity
- total headache days of any severity
- total number of days of use of any acute headache medication
- total number of headache hours of at least moderate severity
- total number of headache hours of any severity
- total number of days with nausea or vomiting
- total number of days with photophobia and phonophobia

Other efficacy baseline values that will be measured on day 0 include

- disability score in patients with CM, as measured by the HIT-6 ([Appendix C](#))
- disability score in patients with EM, as measured by the MIDAS questionnaire ([Appendix D](#))
- quality of life, as measured by the MSQOL questionnaire ([Appendix E](#))
- health status, as measured by the EQ-5D-5L questionnaire ([Appendix G](#))
- patient depression status, as measured by the PHQ-2 and the PHQ-9 ([Appendix I](#))

- patient work productivity and activity impairment, as measured by the WPAI questionnaire ([Appendix J](#))

For safety data, new patient's baseline values will be the last values prior to the 1st dose of study drug.

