Patients who rollover from the pivotal efficacy studies and are eligible to participate in this study will begin this study at visit 2 after completing the informed consent process. Visit 2 may correspond with the end-of-treatment (EOT) visit (visit 5) or it may be a separate visit. For patients who begin this study on the same day as EOT visit (visit 5) for the pivotal efficacy studies, EOT visit procedures/assessments must be completed before beginning visit 2 procedures/assessments. Baseline for patients rolling over from the pivotal efficacy studies refers to the 28-day run-in period (for headache variables only) and visit 2 (day 0) of the pivotal efficacy studies.

Patients randomized to the active treatment groups in the pivotal efficacy studies who continue receiving study drug in the current study will receive the same treatment throughout the current study. Thus, patients with CM who received a loading dose of TEV-48125 at 675 mg followed by monthly sc TEV-48125 at 225 mg and patients with EM who received monthly sc TEV-48125 at 225 mg will continue receiving monthly sc TEV-48125 at 225 mg, and patients with CM or EM who received sc TEV-48125 at 675 mg once in 3 months will continue receiving quarterly sc TEV-48125 at 675 mg.

Patients with CM randomized to the placebo treatment group in the pivotal efficacy study who continue receiving study drug in the current study and patients with CM who are not rolling over from the pivotal efficacy study will be randomized at visit 2 in a 1:1 ratio to receive 1 of 2 treatments:

- sc TEV-48125 at 675 mg (loading dose) followed by 11 monthly sc doses of TEV-48125 at 225 mg
- sc TEV-48125 at 675 mg once every 3 months for 12 months for a total of 4 doses

Patients with EM randomized to the placebo treatment group in the pivotal efficacy study who continue receiving study drug in the current study and patients with EM who are not rolling over from the pivotal efficacy study will be randomized at visit 2 in a 1:1 ratio to receive 1 of 2 treatments:

- monthly sc TEV-48125 at 225 mg for 12 months
- sc TEV-48125 at 675 mg once every 3 months for 12 months for a total of 4 doses

(Note: For this study and the pivotal efficacy studies, monthly dosing refers to dosing approximately every 4 weeks [28 days].)

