5. STUDY POPULATION SUMMARY

5.1. General

The ITT population (ie, randomized population) will be used for all study population summaries unless otherwise noted. Summaries of the efficacy endpoints will be presented by treatment group and overall for CM and EM patients respectively, and total unless otherwise noted. Summaries of the safety endpoints will be presented by treatment group and overall for combined EM and CM patients.

The FAS will be used for all efficacy analyses. Summaries for the FAS population will be presented by treatment group, new patients and placebo-treated rollover patients, active rollover patients, and overall for CM and EM patients.

The safety population will be used for all safety analyses. Summaries for safety population will be presented by treatment group (loading dose of TEV 48125 at 675 mg followed by monthly TEV-48125 at 225 mg, monthly TEV-48125 at 225 mg, and quarterly TEV-48125 at 675 mg) and overall. EM and CM patients will be combined for the safety analysis.

For continuous variables, descriptive statistics (n, mean, SD, SE, median, minimum, and maximum) will be provided. For categorical variables, patient counts and percentages will be provided. Categories for missing data will be presented if necessary.

For the rollover patients, their baseline data refer to the baseline in the pivotal studies.

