7. SAFETY ANALYSIS

7.1. General

The safety population will be used for all safety analyses. The CM and EM patients will be combined if they receive the same treatment. Summaries will be presented by treatment group (loading dose of TEV-48125 at 675 mg followed by monthly TEV-48125 at 225 mg, monthly TEV-48125 at 225 mg, and quarterly TEV-48125 at 675 mg) as actually received and overall. In addition, the patients with CM and patients with EM will be summarized separately for their safety endpoints. The descriptive statistics will be presented by treatment group and visits/months for new patients and placebo-treated rollover patients, TEV-48125-treated rollover patients, and overall under the same treatment, unless otherwise specified.

The safety and tolerability endpoints for this study are as follows:

- occurrence of adverse events throughout the study
- changes from baseline in clinical laboratory (serum chemistry, hematology, coagulation, and urinalysis) test results
- abnormal standard 12-lead ECG findings
- changes from baseline in vital signs (pulse, systolic and diastolic blood pressure, body temperature, and respiratory rate) measurements
- abnormal physical examination findings
- abnormal local injection site tolerability findings (ie, erythema, induration, and ecchymosis) and occurrence of injection site pain
- suicidal ideation and behavior as suggested by the eC-SSRS

Safety and tolerability measures and time points are provided in [Table 1](#) (patients rolling over from the pivotal efficacy studies), [Table 2](#) (patients not rolling over from the pivotal efficacy studies), and [Table 3](#) (patients rolling over from the pivotal efficacy studies for ADA assessment only).

Adverse events collected for the ADA only analysis population will be listed separately.

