7.6. Clinical Laboratory Tests

Clinical laboratory tests (serum chemistry, hematology, coagulation, and urinalysis) will be performed at the time points detailed in [Table 1](#) and [Table 2](#) using the central laboratory. Specific laboratory tests to be performed are listed below in [Table 6](#).

Table 6: Clinical Laboratory Test

Serum chemistry	Hematology	Coagulation	Urinalysis

 • calcium • phosphorus • sodium • potassium • chloride • carbon dioxide • magnesium • glucose • blood urea nitrogen • creatinine • ALT • AST • total bilirubin • direct bilirubin • indirect bilirubin (calculated) • lactate dehydrogenase • GGT • ALP • albumin • creatine phosphokinase • total protein 	
 • hemoglobin • hematocrit • RBC count • RBC indices 
 - mean corpuscular volume - mean corpuscular hemoglobin concentration - RBC distribution width • platelet count • WBC count and differential count (absolute values and percentages) 
 - neutrophils - lymphocytes - eosinophils - monocytes - basophils 	
 • prothrombin time • partial thromboplastin time • INR 	
 • color and appearance • specific gravity • pH • blood (hemoglobin) • glucose • albumin • protein • ketones • leukocyte esterase • nitrite • direct bilirubin • microscopic 
 - bacteria - RBCs - WBCs - casts - crystals

Laboratory tests results and changes from baseline for chemistry, hematology, urinalysis, and coagulation laboratory tests will be summarized by visits for each treatment group using descriptive statistics. Shifts (below, within, and above the normal range) from baseline to each visit and endpoint will be summarized using patient counts.

The incidence of potentially clinically significant abnormal results will be summarized using descriptive statistics with the criteria specified in [Table 7](#). The potentially clinically significant abnormal laboratory values will include all postbaseline values (including scheduled, unscheduled, and early termination visits) for the summaries. Listings of patients who have potentially clinically significant abnormal laboratory data will be presented.

Table 7: Criteria for Potentially Clinically Significant Laboratory Values

Test	Criterion value
Serum chemistry	
ALT	$\geq 3 \times \text{ULN}$
AST	$\geq 3 \times \text{ULN}$

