ALP	$\geq 3 \times \text{ULN}$
GGT	$\geq 3 \times \text{ULN}$
Lactate dehydrogenase	$\geq 3 \times \text{ULN}$
Blood urea nitrogen	$\geq 10.71 \text{ mmol/L}$
Creatinine	$\geq 177 \mu\text{mol/L}$
Uric acid Men	$\geq 625 \mu\text{mol/L}$
Women	$\geq 506 \mu\text{mol/L}$
Bilirubin (total)	$\geq 34.2 \mu\text{mol/L}$
Hematology	
Hematocrit Men	$< 0.37 \text{ L/L}$
Women	$< 0.32 \text{ L/L}$
Hemoglobin Men	$\leq 115 \text{ g/L}$
Women	$\leq 95 \text{ g/L}$
WBC counts	$\leq 3 \times 10^9/\text{L}$ or $\geq 20 \times 10^9/\text{L}$
Eosinophils	$\geq 10\%$
Absolute neutrophil counts	$\leq 1 \times 10^9/\text{L}$
Platelet counts	$\leq 75 \times 10^9/\text{L}$ or $\geq 700 \times 10^9/\text{L}$
Urinalysis	
Blood (HGB)	≥ 2 unit increase from baseline
Glucose	≥ 2 unit increase from baseline
Ketones	≥ 2 unit increase from baseline
Total protein	≥ 2 unit increase from baseline

ALP=alkaline phosphatase; ALT=alanine aminotransferase; AST=aspartate aminotransferase; GGT=gamma-glutamyl transpeptidase; HGB=hemoglobin; INR=international normalized ratio; ULN=upper limit of normal range; WBC=white blood cell

Serum beta-human chorionic gonadotropin (β -HCG) tests will be performed for all women of childbearing potential at screening (visit 1), and urine β -HCG tests will be performed for women of childbearing potential at visits 2 through 5. Positive pregnancy test results will be listed.

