7.7. Vital Signs

Vital signs (pulse, systolic and diastolic blood pressure, body temperature, and respiratory rate) will be measured before other assessments (eg, blood draws and administration of questionnaires) at the time points detailed in [Table 1](#) and [Table 2](#).

For any abnormal vital sign finding, the measurement should be repeated as soon as possible. Any vital sign value that is judged by the investigator as a clinically significant change (worsening) from a baseline value will be considered an adverse event.

Vital signs values and changes from baseline to each visit and endpoint will be summarized using descriptive statistics. The incidence of potentially clinically significant abnormal values will be summarized for selected vital signs using descriptive statistics.

[Table 8](#) specifies the criteria for identifying vital signs as potentially clinically significant abnormal. Note that in order to be identified as potentially clinically significant abnormal, a value would need to meet both conditions below: ie, have a value beyond the criterion value and a change of at least the magnitude specified in the change from baseline column. Summaries of potentially clinically significant abnormal vital signs values will include all postbaseline values (including scheduled, unscheduled, and early termination visits).

Table 8: Criteria for Potentially Clinically Significant Vital Signs

Vital Sign	Criterion value	Change relative to baseline
Pulse	≥ 120 bpm	Increase of ≥ 15 bpm
	≤ 50 bpm	Decrease of ≥ 15 bpm
Systolic blood pressure	≥ 180 mm Hg	Increase of ≥ 20 mm Hg
	≤ 90 mm Hg	Decrease of ≥ 20 mm Hg
Diastolic blood pressure	≥ 105 mm Hg	Increase of ≥ 15 mm Hg
	≤ 50 mm Hg	Decrease of ≥ 15 mm Hg
Respiratory rate	< 10 breaths/min	
Body temperature	$\geq 38.3^\circ\text{C}$	Change of $\geq 1.1^\circ\text{C}$

A listing for clinically significant abnormal vital signs will be presented.

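### The safety baseline for placebo-treated rollover patients predates their placebo period, so off-drug change enters their change-based safety summaries

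*SAP*

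**What the plan says.** SAP 4.2 sets the rule for all rollover patients: "For the patients rolling over from the pivotal efficacy studies, their baseline values will be the baseline values from the pivotal studies". SAP 5.1 repeats it: "For the rollover patients, their baseline data refer to the baseline in the pivotal studies". SAP 2.1, in line with protocol 3.1, says what that baseline is. It "refers to the 28-day run-in period (for headache variables only) and visit 2 (day 0) of the pivotal efficacy studies". For anything other than headache variables, the reference is therefore pivotal day 0.

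The only separate safety rule in SAP 4.2 covers new patients, whose "baseline values will be the last values prior to the 1st dose of study drug".

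SAP 7.1 presents safety data by treatment group. It then adds a breakdown within CM and EM "for new patients and placebo-treated rollover patients, TEV-48125-treated rollover patients, and overall under the same treatment". The natural reading is that new patients and placebo-treated rollovers form one cohort.

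Several safety outputs depend on the baseline:

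- Laboratory changes by visit, and normal-range shifts "from baseline to each visit and endpoint will be summarized using patient counts" (SAP 7.6).
- The four urinalysis flags in Table 7, each a 2-or-more "unit increase from baseline".
- The vital-sign flags in Table 8, where a value must "have a value beyond the criterion value and a change of at least the magnitude specified in the change from baseline column" (SAP 7.7). Respiratory rate has no change condition.
- ECG shifts and changes (SAP 7.8).

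**The concern.** A safety baseline should be tied to first exposure. For rollovers already on TEV-48125, pivotal day 0 does that. For new patients, the last pre-dose value does that. Placebo-treated rollovers are the one dosed group for whom it fails: their first TEV-48125 dose comes at visit 2 of this study, after the whole pivotal placebo period. Whatever happened to blood pressure, pulse or laboratory values on placebo is counted as change in this study. It can create apparent on-drug change or hide real change.

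Changes from baseline in laboratory tests and vital signs are listed safety endpoints under the primary objective. Protocol 1.4.1.1 names effects on blood pressure and heart rate as a potential risk. Patients receiving the drug for the first time are where an early effect should show, and theirs is the cohort with the mixed baseline. The study is uncontrolled and descriptive, and no planned summary separates placebo-period change from on-drug change.

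Carrying the pivotal run-in forward is a reasonable choice for headache endpoints. That reasoning does not extend to laboratory tests, vital signs or ECG.

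**Working it through.** **The plan's own figure.** There is no power calculation to reproduce. The planned enrolment in SAP 2.3 adds up: 867 + 675 + 300 = 1842.

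**Inputs**

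- The rollover baseline for non-headache variables is pivotal visit 2, day 0 (protocol 3.1, SAP 2.1).
- Pivotal end of treatment is visit 5 (protocol 3.1), and monthly dosing means every 28 days in the pivotal studies as well. The placebo period from visit 2 to visit 5 is therefore inferred as 3 × 28 = 84 days.
- In this study's Table 1, rollovers' first on-drug vital signs are at visit 3 (day 28), their first on-drug laboratory tests at visit 4 (day 56), and their only scheduled on-drug ECG at visit 14 (day 336).
- Table 1, footnote d: visit 2 safety tests are repeated only if entry is more than 30 days after pivotal visit 5.

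**Off-drug share of the change interval** = (84 + gap) / (84 + gap + study day)

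| Visit | No gap | 30-day gap | New patients |
|---|---|---|---|
| 3 (day 28) | 84/112 = 75% | 114/142 = 80% | 0% |
| 4 (day 56) | 84/140 = 60% | 114/170 = 67% | 0% |
| 14 (day 336) | 84/420 = 20% | 114/450 = 25% | 0% |

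**Effect on a flag.** The Table 8 high diastolic rule needs a value of at least 105 mm Hg and a rise of at least 15. Take an on-drug value of 105, with illustrative earlier values:

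| Pivotal day 0 | Last pre-dose | Rise, SAP rule | Rise from pre-dose |
|---|---|---|---|
| 88 | 98 | 105 − 88 = 17, flagged | 105 − 98 = 7, not flagged |
| 95 | 85 | 105 − 95 = 10, not flagged | 105 − 85 = 20, flagged |

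The same on-drug reading can be falsely flagged or missed.

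**Weight in the grouped cohort.** The documents do not give the pivotal placebo share, s. Assume that all 867 + 675 = 1542 planned rollovers enter, together with 300 new patients. The share of placebo rollovers is then 1542s / (1542s + 300):

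- s = 1/4: about 386 of 686, 56%
- s = 1/3: 514 of 814, 63%
- s = 1/2: 771 of 1071, 72%

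Under those assumptions, a mean off-drug drift of m units would move the grouped mean change by about 0.56m to 0.72m. The documents give no value for m.

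**The case against.** The strongest defence is that the choice is disclosed, consistent across protocol and SAP, and drug-naive: pivotal day 0 precedes any TEV-48125 in placebo rollovers too, and it keeps their safety changes on the pivotal-study reference. That is true, but it does not justify measuring two halves of one first-exposure cohort from different points.

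Other points stand in part:

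- The percentages describe elapsed time, not bias. A 75% off-drug interval is compatible with no distortion, and the diastolic values are constructed.
- The affected breakdown is additional to the treatment-group totals, where active rollovers dilute the effect.
- SAP 7.6 and 7.7 also summarise actual values by visit, which need no baseline. This helps only partly, because visit 2 values are collected in rollovers only after a gap of more than 30 days.
- Clinically significant worsening is recorded as an adverse event. Rollover exclusions (a) and (c) in protocol 4.2.1 should remove clinically significant laboratory and ECG findings at entry. What remains is mainly smaller drift and normal-range shifts.
- The pivotal protocols and SAPs are not available here, so testing at pivotal end of treatment is implied by Table 1, footnotes b and d, rather than shown.

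These points limit the consequence. None supplies a baseline tied to first exposure for this group.

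**Conclusion.** The concern holds. No passage in either document gives placebo-treated rollovers a safety baseline just before their first TEV-48125 dose. Their laboratory, vital-sign and ECG changes and shifts, the urinalysis flags and the two-condition vital-sign flags therefore include placebo-period change. The affected interval is at least about 84 days, which is most of the elapsed time at the first on-drug vital-sign and laboratory visits and a fifth of it at end of treatment.

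The baseline mismatch is certain from the text. The 84 days rests on the inferred pivotal visit spacing, and the cohort weights rest on an assumed placebo share and full rollover. The size and net direction of any effect on results are unknown. Injection-site assessments, adverse event incidence, the respiratory-rate flag and absolute chemistry or hematology cut-offs applied to on-treatment values are not affected.

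This should be corrected because it touches listed safety endpoints and is cheap to change. It does not undermine the study.

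**What to change.** Add one sentence to SAP 4.2: for safety data, the baseline of a rollover patient who received placebo in the pivotal study is the last value before the first TEV-48125 dose in this study, meaning the pivotal end-of-treatment value, or the visit 2 value where the test was repeated. Keep the pivotal baseline for rollovers already treated with TEV-48125, and leave all efficacy baselines alone. Qualify the general statement in SAP 5.1 to match.

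Record the change in SAP 13, which now declares none, because protocol 3.1 names pivotal visit 2 as the baseline. The SAP preface already says that the SAP prevails where the two differ.

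The cost is these text changes and a derivation flag. No new visits or tests should be needed, subject to confirming that the pivotal end-of-treatment visit included these assessments. The downside is that placebo rollovers' safety changes would no longer be on the pivotal-study baseline. A supplementary table on the pivotal baseline could keep that view.

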4.3. Region of Pooled Countries

The countries will be pooled to 2 regions as [Table 4](#) for the analysis.

Table 4: The Region of Pooled Countries

Region	Country
United States	United States
Other	Japan, Czech Republic, Poland, Russia, Canada, Spain, Israel, Finland

4.4. Multiple Comparisons and Multiplicity

No inferential analysis will be performed in this study.

4.5. Handling Withdrawals and Missing Data

A patient's monthly number of days/hours of efficacy variables during the 4-week period after each dose of study drug will be calculated for months 1, 2, 3, 6 and 12. If a patient has missing diary days when calculating the monthly variables, the following method will be used to handle the missing data.

- If a patient has ≥ 10 days of e-diary data for a month, the monthly number of days/hours of efficacy variables will be prorated to 28 days for that month.
- If a patient has < 10 days of e-diary data for a month, the monthly number of days/hours of efficacy variables will be considered as missing for that month.

The missing questionnaire items handling for the MSQOL questionnaire ([Appendix E](#)) is discussed in [Appendix F](#): scoring instruction for MSQOL.

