if of childbearing potential, patients must meet any of the following criteria:
 - Patients must simultaneously use 2 forms of highly effective contraception methods (defined in Section 5.2) with their partners during the entire study period and for 7.5 months after the last dose of study drug.
 - Sexual abstinence is only considered a **highly effective method** if defined as refraining from heterosexual intercourse in the defined period. The reliability of sexual abstinence needs to be evaluated in relation to the duration of the clinical study and the preferred and usual lifestyle of the subject. Periodic abstinence (eg, calendar, ovulation, symptothermal, post-ovulation methods), declaration of abstinence for the duration of a study, and withdrawal are not acceptable methods of contraception.
- h. Female patients of childbearing potential must have a negative serum β -HCG pregnancy test at screening (confirmed by urine dipstick β -HCG pregnancy test at baseline).

- i. The patient demonstrated compliance with the electronic headache diary during the run-in period by entry of headache data on a minimum of 24 out of 28 days (~85% diary compliance)
- j. The patient is in good health as determined by a medical and psychiatric history, medical examination, 12-lead ECG, serum chemistry, hematology, coagulation, and urinalysis.
- k. The patient must be willing and able to comply with study restrictions, to remain at the clinic for the required duration during the study period, and to return to the clinic for the follow up evaluation as specified in this protocol.

Patients Rolling Over from the Pivotal Efficacy Studies for ADA Assessment Only: Patients may be included in this study if they sign and date the informed consent document.

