- a calendar day (0:00 to 23:59) demonstrating a headache of any duration that was treated with migraine-specific medications (triptans and ergot compounds)

The derivation logic is presented in [Appendix B](#).

In addition, the following questionnaires will be used for the assessments of migraine impairment, quality of life and satisfaction of treatment etc. during the study (See [Table 1](#) and [Table 2](#) for the schedules of the assessments).

- assessment of headache impact in patients with CM using the HIT-6 ([Appendix C](#))
- assessment of headache-related disability based on lost days of activity in 3 domains (work, household work, and nonwork) over the previous 3 months in patients with EM using the MIDAS ([Appendix D](#))
- quality of life, as measured by the MSQOL questionnaire ([Appendix E](#))
- health status, as measured by the EQ-5D-5L questionnaire ([Appendix G](#))
- assessment of patient satisfaction, as measured by the PGIC scale, at 4 weeks after administration of the 1st dose, 3rd dose, 6th dose, 9th dose, and last (12th) dose of study drug ([Appendix H](#))
- patient depression status, as measured by the PHQ-2 and the 9-item PHQ-9 ([Appendix I](#))
- patient work productivity and activity impairment, as measured by the WPAI questionnaire ([Appendix J](#))

The **monthly average** number of days of efficacy variables **during a 4-week period** after each dose at visits 2, 3, 4, 7, and 13 will be derived and normalized to **28** days equivalent for month 1, 2, 3, 6 and 12, respectively, using the following formula, where the monthly data separated by each visit will be used.

$$\frac{\sum \text{Days of efficacy variable during the 4 week period}}{\sum \text{Days with assessments recorded in the eDiary for the 4 week period}} \times 28 \quad (1)$$

The **baseline values** for the patients rolling over from the pivotal Studies TV48125-CNS-30049 and TV48125-CNS-30050 will be carried forward. The **baseline value** for the eligible new randomized patients will be calculated using all data collected in the run-in period, ie,

$$\frac{\sum \text{Days of efficacy variable during the run – in period}}{\sum \text{Days with assessments recorded in the eDiary for the run – in period}} \times 28 \quad (2)$$

The **percentage of reduction** in the monthly average number of an efficacy variable will be calculated as

$$\frac{\text{baseline value} - \text{postbaseline value}}{\text{baseline value}} \times 100\% \quad (3)$$

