6.4.1. Variable Definition

6.4.1.1. Headache Diary Data

The exploratory efficacy variables derived from the headache e-diary data include mean change from baseline in the monthly average number of migraine days, headache days of at least moderate severity, headache days of any severity, days of use of any acute headache medications, headache hours of at least moderate severity, headache hours of any severity, days with nausea or vomiting, days with photophobia and phonophobia *during the 4-week periods* after visits 2, 3, 4, 7, and 13 for months 1, 2, 3, 6, and 12. The change from baseline is calculated as *postbaseline value – baseline value*, where the postbaseline values are derived using formula (1) in Section 6.1 and the baseline values are carried forward from the pivotal studies or calculated using formula (2) in Section 6.1 for new patients

If a patient has missing days of entries in the e-diary for a month, his/her monthly average number of days of study variables *during the 4-week period* for that month will be handled as discussed in Section 4.5.

The percent reduction in the monthly average number of migraine days *during the 4-week period* after each dose at visits 2, 3, 4, 7, and 13 for months 1, 2, 3, 6, and 12 will be calculated by formula (3) in Section 6.1. The patient is considered as a responder reaching 50%, 75%, or 100% reduction if his/her percent reduction is 50% or more, 75% or more, or 100%, respectively. Similar definition will be applied to calculate the proportion of patients reaching at least 50%, 75%, or 100% reduction in the monthly average number of headache days of at least moderate severity during the 4-week period for months 1, 2, 3, 6 and 12. If a patient is early discontinued from the study, he/she will be counted as a non-responder.

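### For patients who stay in the study, missed diary days can only raise the 100% responder rows, because a month with 10 event-free entries is scored as total response

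*SAP*

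**What the plan says.** SAP Section 4.5 sets one completeness rule for all monthly diary variables: "If a patient has ≥ 10 days of e-diary data for a month, the monthly number of days/hours of efficacy variables will be prorated", with a 28-day month as the standard. A month with fewer entries is set to missing. Formula (1) in SAP Section 6.1 divides the event days by "Days with assessments recorded in the eDiary for the 4 week period" and multiplies by 28. Formula (3) turns the result into a percent reduction from baseline.

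SAP Section 6.4.1.1 applies the responder cut-offs to that value: "The patient is considered as a responder reaching 50%, 75%, or 100% reduction if his/her percent reduction is 50% or more", with matching conditions for the other two levels. For missing entries, the monthly value "for that month will be handled as discussed in Section 4.5". The 100% level has no stricter diary minimum. There is one separate rule: "If a patient is early discontinued from the study, he/she will be counted as a non-responder".

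SAP Section 6.4.2.1 reports the 100% row for months 1, 2, 3, 6 and 12 with a 95% confidence interval. It also reports a sustained 100% row over months 3, 6 and 12. Protocol Section 9.5.3 lists sustained response at 50% and 75% only, so the sustained 100% row comes from the SAP. Protocol Section 6.2 closes each diary day after 48 hours, so a missed day cannot be recovered. Protocol Section 9.5.4.2 plans no sensitivity analysis.

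**The concern.** Scaling to 28 days is reasonable for mean day counts: if days are missed at random, the scaled count is right on average. The 50% and 75% cut-offs can also err in either direction. The 100% cut-off behaves differently because it is met only by a count of exactly zero. A missed day can hide an event, but it cannot create one. Among patients who stay in the study with an evaluable month, missed entries can therefore add false total responders to the row and cannot remove true ones.

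At stake is how a reader interprets the monthly and sustained 100% percentages. These are descriptive results, but SAP Section 2.5.1 puts the data up to a cut-off date into an interim report supporting a licence application. As planned, nothing in the tables would show how many total responders had nearly complete diaries and how many had sparse ones.

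**Working it through.** The plan gives no figure of its own for this, so the check applies its formulas directly.

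**Inputs.** Minimum of 10 entries in a 28-day month (SAP 4.5); formulas (1) and (3) (SAP 6.1); cut-offs (SAP 6.4.1.1); run-in diary standard for new patients, "entry of headache data on a minimum of 24 out of 28 days (~85% diary compliance" (Protocol 4.1.2), that is 24/28 = 85.7%. The documents do not give the true number of event days *k*, the pattern of missed days or the distribution of entries *m*. I assume that the recorded days are a random subset of the 28 and show a range.

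**Step 1: the scoring.** With no event in 10 entries, formula (1) gives 0/10 × 28 = 0, and formula (3) gives (baseline − 0)/baseline = 100% at any non-zero baseline. The other 18 days play no part. One event in 10 entries gives 1/10 × 28 = 2.8 days; at an illustrative baseline of 8 days this is (8 − 2.8)/8 = 65%. Only months with no recorded event are affected.

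**Step 2: chance of a false 100%.** The probability that *m* recorded days miss all *k* event days is C(28−k, m)/C(28, m). For k = 1 this is (28 − m)/28. For k = 2 it is (28 − m)(27 − m)/(28 × 27).

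| Entries m | k = 1 | k = 2 |
|---|---|---|
| 10 | 18/28 = 64.3% | 306/756 = 40.5% |
| 14 | 14/28 = 50.0% | 182/756 = 24.1% |
| 20 | 8/28 = 28.6% | 56/756 = 7.4% |
| 24 | 4/28 = 14.3% | 12/756 = 1.6% |
| 28 | 0 | 0 |

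At 10 entries the chance falls to 15.0% for k = 4 and 1.4% for k = 8. At a baseline of 8 days, k = 2 is a true reduction of (8 − 2)/8 = 75%, so the misclassified patients are mostly strong partial responders.

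**Step 3: the sustained row.** All three months must show zero. With 10 entries in each and months treated as independent, the chance is 0.405³ ≈ 7% for k = 2 and 0.643³ ≈ 27% for k = 1.

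**Step 4: the discontinuation rule.** A patient who leaves the study is a non-responder, so a month cut short by withdrawal cannot produce a false total responder. The same rule counts a true total responder who leaves as a failure, which lowers the rate. SAP Section 2.3 anticipates 30% drop-out, so this opposing effect need not be small.

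**The case against.** The strongest case against has four parts.

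- **Sparse months may be rare.** New patients needed 24 of 28 run-in entries. Rollover patients below 75% in the last pivotal month were excluded (Protocol 4.2.1). Entries are accepted up to 48 hours late, and site staff review the diary at visits. This stands: the 40% and 64% figures belong to the 10-entry extreme, and nothing in the documents says how often it occurs.
- **Discontinuers are already failures.** This also stands, and it confines the problem to continuing patients.
- **All efficacy is exploratory.** The primary endpoints are safety, and SAP Section 4.4 rules out inferential analysis. No error rate is affected. The percentages are nevertheless what will be reported.
- **A stricter rule has its own bias.** Counting a patient with 10 to 23 clean entries as a failure would misclassify true total responders. As a hypothetical, with true total response fixed at 10%, a fall from 90% to 60% of patients with enough entries would move the row from 9% to 6%. Replacing the rule would also undo one that the SAP amendment history attributes to FDA comments. It could depart from Protocol Section 9.3, which promises the same diary handling as in the pivotal studies. This is a sound reason to add a row and leave the planned one alone.

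A reader might infer more: that the published 100% rate will be too high overall, that it will drift upward through months 6 and 12, or that 40% of reported total responders are false. The documents support none of these. The discontinuation rule pulls the other way, no diary-completion data are given, and the probabilities are conditional on a given true count and number of entries.

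**Conclusion.** The point holds for continuing patients. Within an evaluable month, missed entries can only push the monthly and sustained 100% rows upward, and the plan shows the reader nothing from which to judge the effect. For one patient-month with 1 or 2 true event days, the chance of a false 100% runs from 64% or 40% at 10 entries to 14% or 1.6% at 24. This rests on days being missed at random. If patients tend to skip entries on headache days the chance is higher, and if they tend to skip headache-free days it is lower.

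The direction and size of the net bias in the reported rate cannot be computed from the documents. Means and the 50% and 75% rows do not share this one-way error. Because the endpoint is exploratory and descriptive, this is a reporting improvement worth making and does not undermine the study.

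**What to change.** Keep the 10-day rule for means, for the 50% and 75% rows and for the planned 100% row, so that the results stay in line with Protocol Section 9.3 and with the rule adopted after FDA comments. In SAP Section 6.4.2.1, beside each 100% row (monthly and sustained):

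1. Add a second row with the same denominator that counts a total responder only if at least 24 of 28 diary days were recorded. Where the dose-to-dose window of SAP Section 4.6 is longer or shorter than 28 days, use the same share of that window.
2. Report the number of patients with zero recorded event days but fewer entries than that.

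The gap between the two rows then shows how far the 100% result depends on sparse diaries. The 24-day standard is the trial's own for new patients. It leaves a residual (14% for 1 true day at 24 entries), so the second row is not a strict lower bound. The 75% standard applied to rollover patients, 21 of 28, would leave more: 7/28 = 25.0% for 1 true day and 42/756 = 5.6% for 2.

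The cost is one derived flag and one extra row per table, with no new data. The second row is conservative because it omits true total responders with sparse diaries, and the table note should say so.
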